#### Handling of participants after permanent intervention discontinuation

If a participant is withdrawn from study intervention permanently, the Sponsor will be notified within 2 business days and the date and reason(s) for the withdrawal will be documented by the Investigator in the appropriate pages of the eCRF when considered as confirmed.

Participants who prematurely discontinue the IMP will be encouraged to complete the rest of study visits for safety and efficacy assessments up to and including the last scheduled visit (Week 106). A separate PK sample may be taken if appropriate. At a minimum, participants should complete an early discontinuation visit 2 weeks after the last IMP dosing. All withdrawn participants will be followed until resolution of all their AEs or until the unresolved AEs are judged by the Investigator or Sponsor to have stabilized (see [Section 10.3.3](#)).

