1.2 OBJECTIVES AND ENDPOINTS

Table 1 - Objectives and endpoints

Part A

Objectives	Endpoints
Primary	

 • To assess the effect of SAR443820 compared to placebo in reducing ALS progression as measured by the Amyotrophic Lateral Sclerosis Functional Rating Scale Revised (ALSFRS-R) 	
 • Change from baseline in the ALSFRS-R total score to Week 24
Secondary	

 • To assess the effect of SAR443820 compared to placebo on a combined assessment of function and survival, respiratory function, muscle strength, and quality of life (QoL) 	
 • Combined assessment of the function and survival (CAFS) score at Week 24
	
 • Change from baseline in slow vital capacity (SVC) to Week 24
	
 • Change from baseline in muscle strength to Week 24
	
 • Change from baseline in Amyotrophic Lateral Sclerosis Assessment Questionnaire (ALSAQ-5) to Week 24
	
 • Change from baseline in serum neurofilament light chain (NfL) to Week 24
	
 • Incidence of adverse events (AE), serious adverse events (SAE), treatment-emergent adverse events (TEAE), potentially clinically significant abnormalities (PCSA) in laboratory tests, electrocardiogram (ECG), and vital signs over 24 weeks
	
 • Plasma concentration of SAR443820

Objectives	Endpoints
	[REDACTED]
	[REDACTED]

• To assess the effects of SAR443820 compared to placebo on neurodegeneration and inflammation disease biomarkers	
• Change from baseline in soluble triggering receptor expressed on myeloid cells-2 (sTREM2) in plasma chitinase-3-like protein-1 (CHI3L1), a selected panel of cytokines and chemokines in serum, and extracellular domain of p75 (p75ECD) in urine to Week 24

Part B

Objectives	Endpoints
Primary	

• To assess the long-term effects of SAR443820 on function and survival	
• Combined assessment of the function and survival (CAFS) score at Week 52
Secondary	

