3 STATISTICAL ANALYSES

3.1 GENERAL CONSIDERATIONS

In general, continuous data will be summarized using the number of observations available, mean, standard deviation (SD), median, interquartile range (Q1, Q3), minimum, and maximum.

Categorical and ordinal data will be summarized using the count and percentage of participants.

Efficacy data will be analyzed in the ITT population, except CAFS endpoints in Part A and Part B will be analyzed in the mITT population. Safety data will be analyzed in the safety population, unless specified otherwise.

In Part A, baseline values are defined as follows. The baseline values of NFL, CHI3L1, the cytokine and chemokine panel in serum, sTREM2 in plasma and $p75^{ECD}$ in urine, are defined as the average value from samples collected at the screening visit and at Day 1 prior to the first dose of the study intervention. For the C-SSRS, the baseline value will be the worst assessment between the past 6 months evaluation at screening and the since last visit evaluation on Day 1. For the other efficacy and safety assessments, the baseline values are defined as the last available value prior to the first dose of study intervention. For participants randomized but not treated, the baseline value is defined as the last available value before randomization. Unless otherwise indicated, 2-sided p-values and 95% confidence intervals [CI(s)] will be provided for efficacy assessment of treatment differences. Unless otherwise specified, analyses will be performed by treatment group (and overall for baseline and demographics characteristics).

Efficacy analyses in Part B will be conducted accumulatively according to the treatment group allocated by randomization in Part A (ie, Placebo/SAR443820 versus SAR443820/SAR443820). Baseline values defined above for Part A will be used as the baseline in the efficacy analyses for Part B, unless otherwise noted. Safety analyses in Part B are stated in [Section 3.6](#).

Observation period

The observation period for safety will be divided into 4 segments:

- The **pre-treatment period** is defined as the period up to first investigational medicinal product (IMP) administration.
- The **on-treatment period** (ie, treatment-emergent (TE) period) **for the Part A** is defined as the period from the first IMP administration to the earliest of 1) last IMP administration + 14 days, 2) first IMP in Part B, 3) death date, or 4) last contact date.

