- The **on-treatment period** (ie, treatment-emergent (TE) period) **for the Part B** is defined as the period from the first IMP administration in Part B to the earliest of 1) last IMP administration + 14 days, 2) death date, or 3) last contact date.
- The **post-treatment period**, if applicable, is defined as the period from the end of the on-treatment period to the last contact date.

The on-study period is defined as the time from randomization until the end of the study defined as the last scheduled visit for those who completed the study and the end-of-study date collected

on electronic case report form (e-CRF) page “Completion of End of Study” for those who did not complete the study. If death is the end-of-study reason, date of death will be used.

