3.6.2 Adverse events

General common rules for adverse events

All adverse events (AEs) will be coded to a lower-level term (LLT), preferred term (PT), high-level term (HLT), high-level group term (HLGT), and associated primary system organ class (SOC) using the Medical Dictionary for Regulatory Activities (MedDRA) version currently in effect at Sanofi at the time of database lock.

The AEs will be analyzed in the following 4 categories:

- Pre-treatment AEs: AEs that developed, worsened or became serious during the pre-treatment period.
- Treatment-emergent adverse events (TEAE)s for Part A: AEs that developed, worsened or became serious during the on-treatment period for Part A

- Treatment-emergent adverse events (TEAE)s for Part B: AEs that developed, worsened or became serious during the on-treatment period for Part B
- Post-treatment AEs: AEs that developed, worsened or became serious during the post-treatment period

Similarly, if occurring, deaths will be analyzed in the pre-treatment, treatment-emergent, and post-treatment periods.

The primary AE analyses will be on TEAEs. Pre-treatment and post-treatment AEs will be described separately.

An AE with incomplete or missing date/time of onset (occurrence, worsening, or becoming serious) will be classified as a TEAE unless there is definitive information to determine it is a pre-treatment or a post-treatment AE.

If the assessment of the relationship to IMP is missing for an AE, this AE will be assumed as related to IMP. Missing severity will be left as missing.

Multiple occurrences of the same event in the same participant will be counted only once in the tables within a treatment period, using the maximum (worst) severity by treatment phase.

The AE tables will be sorted as indicated in [Table 4](#).

Table 4 - Sorting of AE tables

AE presentation	Sorting rules
SOC and PT	By the internationally agreed SOC order and decreasing frequency of PTs ^a
AESI category and PT	By AESI category (protocol order) and decreasing frequency of PTs ^a
PT	By decreasing frequency of PTs ^a

^a Sorting will be based on the SAR443820 treatment group incidence, alphabetic order in case of equal frequency.

Analysis of all adverse events in Part A and Part A + Part B

The overview of TEAE will be generated presenting the number (%) of participants with:

- Any TEAE
- Any severe TEAE
- Any treatment-emergent SAE
- TEAE leading to death
- Any TEAE leading to permanent intervention discontinuation of IMP

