- Any treatment-emergent AESI
- Any TEAE considered by the investigator as related to IMP

An additional overview summary including the number and rate of events will be provided.

The AE summaries of [Table 5](#) will be generated with number (%) of participants experiencing at least one event.

Listings of SAEs from randomized participants, AEs from participants who are treated but not randomized, AEs leading to treatment/study discontinuation and severe AEs will be provided.

Table 5 - Analyses of adverse events

Type of AE	MedDRA levels
All TEAEs	Primary SOC and PT
Common TEAE ($\geq 2\%$ in any group)	PT
TEAEs related to IMP as per Investigator's judgment	Primary SOC and PT
TEAE by maximal intensity	PT
Treatment emergent SAEs	Primary SOC and PT
Treatment emergent SAEs related to IMP as per Investigator's judgment	Primary SOC and PT
Treatment emergent AESIs	AESI category and PT
TEAEs leading to permanent intervention discontinuation	Primary SOC and PT
TEAEs leading to death ^b	Primary SOC and PT
Pretreatment AEs	Overview ^a
Post-treatment AEs	Primary SOC and PT
	Overview ^a
	Primary SOC and PT

^a Will include the following AE categories: any AEs, any serious AEs, any AEs leading to death, any AEs leading to permanent intervention discontinuation

^b Death as an outcome of the AE as reported by the Investigator in the AE page

Analysis of deaths in Part A and Part A + Part B

In addition to the analyses of deaths included in [Table 5](#), the number (%) of participants in the following categories will be provided:

- Deaths during the treatment-emergent period and post-treatment period
- Deaths in non-randomized participants or randomized but not treated participants

Analysis of adverse events of special interest (AESIs) in Part A and Part A + Part B

Adverse events of special interest (AESIs) will be selected for analyses as indicated in [Table 6](#). Number (%) of participants experiencing at least one event will be provided for each event of interest. Tables will be sorted as indicated in [Table 4](#). A listing of AESIs will also be provided.

Table 6 - Selections for AESIs

AESIs	Selection
Pregnancy of a female participant or female partner of a male participant	Dedicated CRF page (AECAT="PREGNANCY DATA")
Symptomatic overdose (serious or non-serious) with IMP	Dedicated CRF page (AECAT="OVERDOSE DATA"; must be symptomatic and AESI marked "Y")
Convulsions	CMQsn00079 for selection and AESI marked "Y"

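### The Part A death and post-treatment AE tables use a post-treatment period with no Week 24 limit, so their crude percentages mix unequal follow-up and do not match the 24-week safety endpoint

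*SAP*

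**What the plan says.** SAP 3.1 states that "The observation period for safety will be divided into 4 segments": pre-treatment, on-treatment for Part A, on-treatment for Part B, and post-treatment. Only the on-treatment time is split by part. The Part A on-treatment period ends at the "earliest of 1) last IMP administration + 14 days, 2) first IMP in Part B, 3) death date, or 4) last contact date". The post-treatment period is defined once and "is defined as the period from the end of the on-treatment period to the last contact date".

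SAP 3.6.2 then uses that period in Part A outputs. Post-treatment AEs are "AEs that developed, worsened or became serious during the post-treatment period", and Table 5 summarises them under a heading that covers both Part A and Part A + Part B. The death section is headed "Analysis of deaths in Part A and Part A + Part B" and gives the number and percentage of participants with "Deaths during the treatment-emergent period and post-treatment period".

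The Part A safety endpoint in SAP Table 1 is an incidence that ends "electrocardiogram (ECG), and vital signs over 24 weeks". Protocol 7.1.1 encourages participants who stop IMP early to attend visits "up to and including the last scheduled visit (Week 106", and footnote b of the Part A schedule keeps AE and SAE review going for them. Since 5 December 2023, participants who finish Part A may roll over for visits but take no SAR443820 (SAP 1.1).

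**The concern.** A table labelled Part A should describe the same 24 weeks for everyone. Under the written definitions it does not:

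- **Early stoppers who stay in follow-up** remain in the post-treatment period from 14 days after the last dose to last contact, well past Week 24.
- **Completers with no Part B dose** have no first Part B IMP date to close the on-treatment period. It runs to last dose + 14 days, and post-treatment time then follows to last contact.
- **Dosed rollovers** move into the Part B on-treatment segment. Post-treatment time starts for them only 14 days after the last Part B dose.

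The outputs are crude percentages with no person-time, so longer observation means more events. Stopping could differ by arm: Protocol 2.3.1 lists ALT increase/DILI as an identified risk, and Protocol 7.1.1 makes discontinuation mandatory when the liver stopping criteria are met. Part A data also feed the decision on whether Part B dosing resumes (Protocol 4.1).

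The Part A + Part B safety tables do not fill the gap. Under SAP 3.6 their categorical groups cover data during SAR443820 exposure, and the placebo-first group contains only participants who went on to take SAR443820.

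**Working it through.** **1. The plan's own timeline.** 4 + 24 + 80 + 2 = 110 weeks including screening, so Week 106 from Day 1. This reproduces the stated duration.

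**2. How far follow-up can reach at the Part A lock.** The first randomization was on 28-Apr-2022 (SAP version history). All participants were past Week 19 on 5-Dec-2023 (Protocol amendment 05 summary).
- Latest randomization: 5-Dec-2023 − 19 weeks = 25-Jul-2023.
- Last Week 24 visit: 5-Dec-2023 + 5 weeks = 9-Jan-2024.
- First participant on that day: 621 days / 7 = Week 88.7, or 89.1 with the 3-day visit window.
- The same participant reaches Week 106 on 9-May-2024, after a lock taken at that point.

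**3. The other two groups on 9-Jan-2024.** Completers who reach Week 24 on or after 5-Dec-2023 have at most 5 weeks beyond it, the first two still on-treatment. For a rollover dosed up to the pause, on-treatment time ends on about 19-Dec-2023, so post-treatment time reopens for about 21 days.

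**4. Size for deaths (assumed inputs).** The documents give only a 20% overall drop-out rate. Assumptions:
- the same hazard λ in both arms, 0.1 to 0.3 deaths per person-year;
- stopping in 20-25% (SAR443820) v 10% (placebo), between Weeks 2 and 22;
- a share r = 0.8 of stoppers kept in follow-up;
- follow-up at lock uniform from Week 24 to Week 88.7, so up to U = 64.7/52 = 1.244 years beyond Week 24.

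Let Δ be the difference in stopping proportion.
- Alive at Week 24: S = exp(−λ × 24/52).
- Mean chance of death between Week 24 and lock: D = 1 − (1 − exp(−λU))/(λU).
- Mean chance that a stopper lost to follow-up dies unseen before Week 24: L, the average of exp(−λ(t+2)/52) − S over stop weeks t from 2 to 22.
- Spurious gap = Δ·r·S·D − Δ·(1−r)·L.

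| λ | Δ | S | D | L | Gap (points) |
|---|---|---|---|---|---|
| 0.1 | 0.10 | 0.955 | 0.060 | 0.019 | 0.46 − 0.04 = 0.4 |
| 0.2 | 0.10 | 0.912 | 0.115 | 0.036 | 0.84 − 0.07 = 0.8 |
| 0.3 | 0.15 | 0.871 | 0.165 | 0.052 | 1.73 − 0.16 = 1.6 |

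In the middle row, SAR443820 deaths counted after Week 24 are 174 × 0.20 × 0.8 × 0.912 × 0.115 = 2.9; for placebo, 87 × 0.10 × 0.8 × 0.912 × 0.115 = 0.7.

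**5. Simulation.** With the middle-row inputs, 1,500 simulated trials of 174 v 87 gave total deaths of 10.3% v 9.5% counted to last contact and 8.7% v 8.7% cut at Week 24. Over the whole range the gap was about 0.3 to 1.6 points.

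A separate simulation (hazards 0.1 to 0.3, stop times uniform over Weeks 0-22) gave these death-proportion ratios, SAR443820 to placebo, at the Part A lock:
- 20% v 20% stopping: about 1.0.
- 20% v 10%, all stoppers followed: 1.10-1.11.
- 30% v 10%, all followed: 1.19-1.23.
- Unequal stopping as above, half the stoppers followed: 1.02-1.07.
- Cut at Week 24, all followed: about 1.0.

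**The case against.** The strongest reply is that this is a missing clarification rather than a biased rule. The endpoint is tied to 24 weeks and SAP Appendix 2 speaks of a Part A study period, so a programmer might apply a Week 24 limit anyway. That is possible. But the only definition written down runs to last contact, and an unwritten limit cannot be relied on.

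Several stronger readings are tempting, and the reply is right that the documents do not support them:

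- **That stoppers are followed to Week 106 in the Part A tables.** SAP 3.8 runs the Part A analyses from the Part A lock, where about Week 88-89 is the ceiling. Week 106 would matter only if Part A tables were rerun at a later lock.
- **That the SAP cuts rolled-over participants at the first Part B dose in these tables.** That cut is written only for the Part A on-treatment period. Read literally, the single post-treatment period reopens after the last Part B dose + 14 days. This still does not give a 24-week table.
- **That the arm with more stoppers shows more events by construction.** The gap needs unequal stopping and stoppers who stay. Someone whose last contact is the visit 2 weeks after the last dose adds almost no post-treatment time.
- **That this is the only comparison of deaths in the Part A report.** CAFS at Week 24 ranks deaths between randomized arms and stands first among the secondary endpoints in the testing order. Redacted tertiary endpoints may add others.
- **That the SAP promises one pooled death total.** Its general rules analyse deaths by period, so the totals in the working are an illustration. Separate rows would show which deaths were off drug, but the post-treatment row would still include deaths after Week 24.

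The size is also modest. A gap of 0.8 points is less than one placebo death (1/87 = 1.15 points). It is about 0.2 of the standard error of the difference at 10% mortality: √(0.09/174 + 0.09/87) = 3.9 points. Safety tables are descriptive and untested.

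**Conclusion.** The point holds as a defect of definition with a modest, conditional effect. The written post-treatment period lets Part A death and post-treatment AE tables count events after Week 24 for some participants and not for others. That departs from the 24-week endpoint whatever the stopping pattern.

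A spurious difference between arms appears only if stopping is unequal and stoppers remain in follow-up. For deaths it is then roughly 0.3 to 1.6 percentage points under the assumed hazards, 20-25% v 10% stopping and 80% retention. It shrinks with lower retention and vanishes with equal stopping. None of the by-arm inputs is in the documents, and the size for post-treatment AEs was not estimated.

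The TEAE tables, which are the primary AE analysis and include TEAEs leading to death, stop at last dose + 14 days at the latest and are not affected.

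**What to change.** In SAP 3.1 and 3.6.2:

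1. For Part A tables, end the post-treatment period at the earliest of first Part B IMP, death, last contact, and the later of (a) the Week 24 date and (b) the end of the Part A on-treatment period (last dose + 14 days).
2. Show treatment-emergent and post-treatment deaths in separate rows.
3. Add one by-arm row of all deaths from first dose to Day 169 regardless of IMP status, with a Kaplan-Meier estimate or person-time.
4. State that participants who rolled over without a Part B dose follow the same rule.
5. List later off-drug deaths and AEs in a separate by-arm table in the Part A + Part B outputs.

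The later-of condition in item 1 is needed because a plain Day 169 cut fails. The last double-blind dose is due the day before the Week 24 visit (Protocol Part A schedule, footnote a). A completer with no Part B dose is therefore on-treatment to about Day 168 + 14 = 182, and a Day 169 cut would end post-treatment time before it starts. Anyone stopping after about Week 22 has the same problem. Under the proposed rule such participants simply have no Part A post-treatment time, while a participant stopping at Week 8 has it from Week 10 to Week 24.

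The cost is SAP wording, one date condition, one extra row and one extra table. No new data are needed.

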### **8.3.8 Adverse event of special interest**

An AESI is an AE (serious or nonserious) of scientific and medical concern specific to the Sponsor's product or program, for which ongoing monitoring and immediate notification by the Investigator to the Sponsor is required. Such events may require further investigation in order to characterize and understand them. Adverse events of special interest may be added, modified or removed during a study by protocol amendment.

For AESIs, the Sponsor is to be informed immediately (ie, within 24 hours), as per the SAE notification guidelines described in Appendix 3 ([Section 10.3](#)), even if a seriousness criterion is not met, using the corresponding pages of the case report form or screens in the eCRF:

- Pregnancy of a female participant who has taken the IMP at least once as well as pregnancy occurring in a female partner of a male participant who has taken the IMP at least once during this study
  - Pregnancy will be qualified as an SAE only if it fulfills 1 of the seriousness criteria (see Appendix 3 [[Section 10.3](#)]).
  - In the event of pregnancy in a female participant, the IMP should be discontinued.
  - Follow-up of the pregnancy in a female participant or in a female partner of a male participant is mandatory until the outcome has been determined (See Appendix 4 [[Section 10.4](#)]).
- Symptomatic overdose (serious or nonserious) with IMP
  - An overdose (accidental or intentional) with the IMP is an event suspected by the Investigator or spontaneously notified by the participant (not based on a systematic pill count) and defined as at least 3 tablets of the IMP taken within 12 hours.
  - Note: An asymptomatic overdose has to be reported as a standard AE.
- Other project-specific AESIs
  - Convulsions.
  - Serious infections meeting SAE definitions criteria (please see [Section 10.3.2](#) for SAE definitions).
  - Increase in ALT  $>3.0 \times$  ULN (confirmed at retest): see the “Increase in ALT algorithm” flow chart in Appendix 6 ([Section 10.6](#)).

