Serious infections meeting SAE definitions criteria	SOC of Infections and Infestations, both AESER and AESI marked "Y"
Increase in ALT > 3 x ULN	Dedicated CRF page (AECAT="ALT INCREASE DATA") and AESI marked "Y"

3.6.3 Additional safety assessments**3.6.3.1 Laboratory variables, vital signs and electrocardiograms (ECGs)**

The following laboratory variables, vital signs and electrocardiogram (ECG) variables will be analyzed. They will be converted into standard international units and conventional unit, if applicable.

- Hematology:
 - Red blood cells and platelets and coagulation: hemoglobin, hematocrit, mean corpuscular volume, mean corpuscular hemoglobin, red blood cell count, platelet count
 - White blood cells: white blood cell count, neutrophils, lymphocytes, monocytes, basophils, eosinophils
- Clinical chemistry:
 - Metabolism: glucose, total protein, albumin, creatine phosphokinase
 - Electrolytes: sodium, potassium, calcium
 - Renal function: creatinine, blood urea nitrogen
 - Liver function: alanine aminotransferase, aspartate aminotransferase, alkaline phosphatase, total and direct bilirubin
 - Pregnancy test: Serum β -human chorionic gonadotropin (all female participants)

- Hepatitis screen: human immunodeficiency virus antibody, hepatitis B surface antigen, hepatitis C virus antibody
- Urinalysis:
 - Urinalysis for quantitative analysis: pH, specific gravity, proteins, glucose, blood, ketones, bilirubin, urobilinogen, nitrite, leukocyte esterase (by dipstick)
- Vital signs: heart rate, systolic and diastolic blood pressure, weight, respiratory rate, temperature
- ECG variables: heart rate, PR, QRS, QT, and corrected QTc (according to Bazett and Fridericia)

Data below the lower limit of quantitation/detection limit (LLOQ) will be replaced by half of the LLOQ, data above the upper limit of quantification (ULOQ) will be replaced by ULOQ value for quantitative analysis.

Quantitative analyses

When relevant, for laboratory variables, vital signs and ECG variables above, descriptive statistics for results and changes from baseline will be provided for each analysis visit window during the on-treatment period for Part A and Part A + Part B. These analyses will be performed using central measurements only (when available) for laboratory variables.

For each laboratory parameter, vital sign parameter and ECG parameter, mean changes from baseline with the corresponding standard error will be plotted over time.

Analyses according to PCSA

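### SAP Table 6 counts four of the five AESI categories only when an AESI flag is set, a condition the protocol does not contain, so unflagged qualifying events drop out of the AESI outputs but not out of the report

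*SAP*

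**What the plan says.** Protocol 8.3.8 names the project-specific AESIs by what happened to the participant: convulsions, "Serious infections meeting SAE definitions criteria", and ALT above 3 x ULN confirmed at retest. Pregnancy and symptomatic overdose are also AESIs. Protocol 9.4.6.1 says that treatment-emergent AESIs are identified by preferred term or a prespecified grouping. Neither section mentions a flag.

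SAP 3.6.2, Table 6, sets the selection rules used in the analysis:

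- Serious infections: "SOC of Infections and Infestations, both AESER and AESI marked 'Y".
- Convulsions: "CMQsn00079 for selection and AESI marked 'Y".
- ALT increase: "Dedicated CRF page (AECAT='ALT INCREASE DATA') and AESI marked 'Y".
- Symptomatic overdose: the dedicated page, and it "must be symptomatic and AESI marked 'Y".
- Pregnancy: "Dedicated CRF page (AECAT='PREGNANCY DATA", with no flag condition.

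These selections drive the counts: "Number (%) of participants experiencing at least one event will be provided for each event of interest". A listing of AESIs follows the same selection. Neither the SAP version history nor SAP 3.9 mentions the flag as a change from the protocol.

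**The concern.** An AND condition on a data-entry field makes the count depend on that field being completed. An event that meets the protocol definition but carries no flag is excluded. The SAP gives no fallback rule, no reconciliation of the flag against coded terms or laboratory values, and no listing of unflagged events.

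This runs against the SAP's own approach to incomplete data. In SAP 3.6.2 an AE with an unclear onset date is treated as treatment-emergent unless there is definite information otherwise, and an AE with no causality assessment is treated as related. A missing AESI flag works the other way and excludes the event.

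At stake is whether the AESI count matches the protocol definition and agrees with the other safety tables in the same report. The affected categories include ALT increase, an identified risk in protocol 2.3.1, and convulsions, a potential risk in the same section.

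**Working it through.** The documents give no AESI rate and no flag completeness, so there is no planned figure to reproduce. The check is a comparison of rules, followed by an illustration under stated assumptions.

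**Step 1. Compare the rules.** For serious infection, take three yes/no facts: infection SOC, serious, flagged. With the infection SOC as the working form of the protocol definition, the protocol requires SOC and serious, and the SAP requires SOC and serious and flagged. Over all eight combinations the two differ in exactly one: SOC yes, serious yes, flag not Y. That event is an AESI under the protocol and is excluded by the SAP. Here the flag can only remove qualifying cases.

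The other categories are less clear-cut:

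| AESI | Protocol 8.3.8 | SAP Table 6 | Possible role of the flag |
|---|---|---|---|
| Serious infection | Infection meeting SAE criteria | SOC, serious, flag | Only removes qualifying cases |
| Convulsions | Convulsions | CMQ, flag | Removes unflagged true cases; may also screen out non-convulsive terms in the CMQ |
| ALT increase | Above 3 x ULN, confirmed at retest | Dedicated page, flag; confirmation not mentioned | Removes unflagged confirmed cases; may also screen out unconfirmed entries |
| Symptomatic overdose | Overdose with symptoms | Dedicated page, symptomatic, flag | Page plus symptoms appears to cover the definition already |
| Pregnancy | Participant or partner pregnancy | Dedicated page | No flag required |

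**Step 2. Where an unflagged event still appears.** SAP Table 5 plans all TEAEs and all treatment-emergent SAEs by SOC and preferred term, without the flag. The infections SOC row of the SAE table is the serious-infection count. SAP 3.6.3.1 plans PCSA analyses from local and central measurements, a Kaplan-Meier analysis of ALT or AST above 3 x ULN, a plot of peak ALT against peak bilirubin, and a summary by ALT above 3, 5, 10 and 20 x ULN. None of these needs the flag or the page. Unflagged convulsions appear in the TEAE tables, but under separate preferred terms: Table 6 is the only planned selection that pools them by the CMQ.

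**Step 3. Size, by assumption.** Let p be true AESI incidence, f the share of true AESIs that carry the flag, and n the planned arm size (174 SAR443820, 87 placebo, SAP 1.1).

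Reported incidence = p × f; expected participants counted = n × p × f. With p = 10% (assumed):

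| f (assumed) | Reported incidence | Of 174 | Of 87 |
|---|---|---|---|
| 100% | 10.0% | 17.4 | 8.7 |
| 95% | 9.5% | 16.5 | 8.3 |
| 90% | 9.0% | 15.7 | 7.8 |
| 80% | 8.0% | 13.9 | 7.0 |
| 70% | 7.0% | 12.2 | 6.1 |

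The chance of losing at least one of k true cases, if flagging is independent between cases, is 1 − f^k. With f = 90%:

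- k = 9 (5% of 174 = 8.7, rounded): 1 − 0.90^9 = 0.61.
- k = 17 (10% of 174 = 17.4, rounded): 1 − 0.90^17 = 0.83.

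At f = 100% it is 0.

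**Step 4. Effect on the comparison.** Assume true rates of 10% and 4% and the same f in both arms. At f = 80% they read as 8.0% and 3.2%; at f = 95%, as 9.5% and 3.8%. The risk difference falls from 6.0 points to 4.8 or 5.7. The risk ratio stays at 2.5 (10/4 = 8.0/3.2 = 9.5/3.8).

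**The case against.** The strongest reply is that little is lost. A reader might infer from Table 6 that unflagged serious infections, convulsions and ALT elevations disappear from the trial's safety reporting. Step 2 shows that they do not. For the liver, the laboratory-based analyses are fuller than the AESI table. This part of the reply stands and limits the point to the AESI overview line, table and listing.

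A reader might also infer that the rule distorts the decision on resuming dosing in Part B. The documents do not support that. Protocol 1.1 and 4.1 tie the decision to a DMC recommendation once Part A data are available. They do not say that the DMC will use Table 6, and the DMC's procedures are in a charter that is not in these documents.

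The flag may also be well completed. Protocol 8.3.8 requires AESI notification within 24 hours, and protocol 10.1.7 and 10.1.8 provide for data quality checks and source verification. Reconciliation rules may sit in data-management documents not provided. This stands as a reason to expect a small loss, but it does not remove the mismatch in the rule. Nor does the SAP say who sets the flag: that the site does so is an inference from the notification process.

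Finally, for convulsions and ALT the flag may do useful work, standing in for CMQ specificity and for confirmation at retest. That is a fair reason not simply to delete it there. It does not apply to serious infections, where SOC and seriousness already express the definition.

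**Conclusion.** The mismatch is real and its direction is certain for serious infections: the Table 6 rule can only undercount relative to the protocol. For convulsions, ALT increase and symptomatic overdose, qualifying events without the flag are likewise dropped, although for convulsions and ALT the flag may also remove some events that should not count. Pregnancy is unaffected.

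The consequence is modest. The AESI outputs may be lower than the SAE table or the laboratory analyses in the same report, with no planned explanation, and unflagged convulsions would have no pooled total. The size depends wholly on flag completeness, which the documents do not give. The rates in the working are assumptions, and the loss is zero if every qualifying event is flagged. These are descriptive summaries with no testing planned (SAP 3.6), so no inferential result is affected.

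**What to change.** Amend SAP Table 6 as follows:

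- **Serious infections:** select by SOC Infections and Infestations with AESER = Y alone.
- **Convulsions:** count by the CMQ irrespective of the flag, with the flagged subset as a second line.
- **ALT increase:** select from the dedicated page irrespective of the flag, and state the protocol's confirmation at retest as a condition.
- **All categories:** add a listing of every case where the flag or page disagrees with the protocol definition. Include confirmed laboratory ALT above 3 x ULN with no AESI record. Symptomatic overdoses without the flag would also be shown here.

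A laboratory-only ALT case belongs in the listing, not in the AESI table. It has no AE record and no preferred term, and that table is built by category and preferred term. Confirmation at retest needs a short programming rule, including how to treat a case that could not be retested in the time that protocol 10.6 allows.

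The cost is a few lines in Table 6, one listing and minor programming. The convulsion CMQ line may pick up a few non-convulsive terms, which the flagged line makes visible. No new data are needed.
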